2.2. Study Endpoints

2.2.1. Primary Endpoint:

- Objective radiographic response (ORR), as measured by modified Response Assessment in Neuro-Oncology (RANO) criteria

2.2.2. Secondary Endpoints:

- Safety and tolerability will be assessed by monitoring frequency, duration, and severity of adverse events (AEs) through physical examinations, by evaluating changes in vital signs, and through clinical laboratory evaluations.
- OS, defined as the time from date of enrollment until death from any cause
- PFS, defined as the time from date of enrollment until the earliest date of disease progression (as determined by modified RANO criteria) or death due to any cause

2.2.3 Exploratory Endpoints:

- Comparison of the following immunocorrelative assays in subjects treated with INCMGA00012 + INCAGN01876, with or without SRS:
 - Multiplex immunohistochemistry on tumor tissue for CD4/8 T cell infiltration, Foxp3+ Treg infiltration, and PD-1/PD-L1 expression
 - Tumor cell and immune cell GITR expression by a validated immunohistochemistry stain
 - Flow cytometry/mass cytometry in tumor tissue and peripheral blood for T cell and monocyte phenotyping
 - RNA-Seq on tumor tissue for PD-1/PD-L1 and GITR expression, T cell- and interferon- γ -related gene expression, and cell-cycle-related gene expression
 - T cell receptor sequencing in tumor tissue and peripheral blood for assessment of TCR clonal diversity
- Association between the above tumor tissue and peripheral blood-based markers of immune activation, tumor genetic mutations, and clinical outcomes of OS, PFS, and ORR
- PK parameters for INCAGN01876 in patients with glioblastoma
- Detection of anti-drug antibodies (ADA) against INCAGN01876

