In both surgical sub-arms, within 7 days of enrollment the subject will receive a single dose of the investigational systemic agent(s) according to the sub-arm to which he/she is assigned. In sub-arm # 1 (INCMAG00012 + INCAGN01876 + SRS), within 3 to 7 days following the neoadjuvant doses of the systemic study drugs, the subject will receive SRS, administered over the course of 3 consecutive business days (8 Gy x 3 fractions, one fraction per day, total dose 24 Gy). Subjects may receive 3 fractions every other day (non-consecutively) for logistical reasons relating to COVID-19. Within 7-14 days following administration of the study drug(s) (surgical sub-arms # 2) or within 7-14 days following SRS (surgical sub-arm # 1), the subject will undergo maximal safe surgical resection of the tumor. Following surgery, the subject will then resume systemic therapy with BOTH investigational agents INCMGA00012 and INCAGN01876 (regardless of which of the two sub-arms the subject was assigned to). The systemic agents should be started as soon as the investigator feels the subject has recovered adequately from surgery, but must be restarted within 5 weeks (35 days) from the date of surgery. Subjects will continue on combined systemic treatment (INCMGA00012 500 mg IV every 4 weeks and INCAGN01876 300mg IV every 2 weeks) until disease progression, unacceptable AEs, or for 2 years, whichever occurs first.

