Day (and window)	-14 to 1	1	5 ± 2	Within 1 day of surgery	Up to 3 days from surgery	1 ± 2	8	15 ± 2	1 ± 2	15 ± 2	1 ± 2	15 ± 2	1 ± 2	
Informed Consent	X													
Review Inclusion /Exclusion Criteria (Section 4)	X													
Karnofsky Performance Status (Section 7)	X	X				X		X	X	X	X	X		X
Demographics/ Medical History (Section 7)	X													
Physical Assessment(targeted after screening (Section 7)	X	X				X		X	X	X	X	X	X	X

Study Week	Screen	Neo-adjvant week		Peri-op weeks		W1	W2	W3	W5	W7	Q 4 weeks		Q 8 weeks	EOT§
		Neo-adjvant cycle		Pre-Op	Post-Op	Cycle 1	Cycle 1	Cycle 1	Cycle 2	Cycle 2	Cycle X	Cycle X	Cycle X (pre-odd cycles only)	
Day (and window)	-14 to 1	1	5 ± 2	Within 1 day of surgery	Up to 3 days from surgery	1 ± 2	8	15 ± 2	1 ± 2	15 ± 2	1 ± 2	15 ± 2	1 ± 2	
Vital Signs: BP, HR, RR (Section 7)	X	X		X		X		X	X	X	X	X		X
ECG (Section 7)	X													
Weight (Section 7)	X	X				X			X		X			X
Height (Section 7)	X													
Pregnancy Test (Section 7; within 7d of first dose of study drug)	X										X			X
Concomitant Medications (Section 7)	X	X		X		X		X	X	X	X	X		X
Clinical Laboratory Evaluation – non-endocrine (CBC, CMP, Mag, Phos, LDH) (Section 7; within 7d of first dose of study drug; Labs can be collected up to -3 days prior to treatment)	X	X			X	X		X	X	X	X	X		X

Study Week	Screen	Neo-adjvant week		Peri-op weeks		W1	W2	W3	W5	W7	Q 4 weeks		Q 8 weeks	EOT§
		Neo-adjvant cycle		Pre-Op	Post-Op	Cycle 1	Cycle 1	Cycle 1	Cycle 2	Cycle 2	Cycle X	Cycle X	Cycle X (pre-odd cycles only)	
Day (and window)	-14 to 1	1	5 ± 2	Within 1 day of surgery	Up to 3 days from surgery	1 ± 2	8	15 ± 2	1 ± 2	15 ± 2	1 ± 2	15 ± 2	1 ± 2	
Clinical laboratory Evaluation – endocrine (TSH, T4) (Section 7) Labs can be collected up to -3 days prior to treatment.	X					X							X	X
Urinalysis (Section 7)	X													X
HBV/HCV screening (Section 7)	X													
Blood collected for INCAGN01876 PK (Section 7)						X***	X	X		X	X†	X***†		
Blood collected for INCAGN01876 ADA (Section 7)						X		X		X		X		
Blood collected for correlatives (Section 7)		X				X			X				X	X

Study Week	Screen	Neo-adjvant week		Peri-op weeks		W1	W2	W3	W5	W7	Q 4 weeks		Q 8 weeks	EOT§
		Neo-adjvant cycle		Pre-Op	Post-Op	Cycle 1	Cycle 1	Cycle 1	Cycle 2	Cycle 2	Cycle X	Cycle X	Cycle X (pre-odd cycles only)	
Day (and window)	-14 to 1	1	5 ± 2	Within 1 day of surgery	Up to 3 days from surgery	1 ± 2	8	15 ± 2	1 ± 2	15 ± 2	1 ± 2	15 ± 2	1 ± 2	

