Adverse Event / Unanticipated Problems Assessment (Section 7)	X	X		X	X	X		X	X	X	X	X		X
INCMGA00012 Administration (Section 5)		X††				X			X		X			
INCAGN01876 Administration (Section 5)		X††				X		X	X	X	X	X		
MRI brain (tumor assessment by mRANO criteria) (Section 7)	X												X*	X†††
SRS planning** (Section 5)	X													
SRS delivery** (Section 5)			X											
Surgical Resection; tissue for correlatives (Section 7)				X										

* MRI scan should be performed within 7 days prior to the cycle start (and ideally within 3 days prior). Adjustments to this 7-day window are allowable per the treating physician’s discretion; however restaging scans MUST BE performed and reviewed before the subsequent cycle’s dose may be initiated

**SRS delivery: Total 24 Gy delivered over 3 consecutive days (8 Gy per day). Subjects may receive 3 fractions every other day (non-consecutively) for logistical reasons relating to COVID-19. Must start between 3 and 7 days after first dose of study drugs

*** PK samples for INCAGN01876 collected pre-dose and at end of infusion on Cycle 1 Day 1 and Cycle 3 Day 15. All other PK draws for INCAGN01876 are pre-dose.

† After the first 2 cycles, PK samples for INCAGN01876 are drawn only on Cycle 3 Day 15, Cycle 4 Day 1, Cycle 4 Day 15, and then only on day 15 of each cycle starting with Cycle 5

†† For the neoadjuvant dose(s) of study drugs INCMGA00012 and INCAGN01876, the subject will be assigned to receive the combination of INCMGA00012 and INCAGN01876, or the combination of INCMGA00012 and INCAGN01876 plus SRS. After surgery ALL subjects will resume the combination of both INCMGA00012 and INCAGN01876

††† MRI and mRANO assessment at EOT are only necessary if this has not already been performed within 28 days of the EOT visit
§ EOT visit occurs within 14 days from when the subject is taken off study

Table 10: Schedule of study procedures, FOLLOW-UP			
Procedure	Safety visit	Safety follow-up	Disease Status and Survival
	30 d after EOT (+/- 7 d)	12 W (+/-14 d) after EOT	Q12W after EOT (+/- 14d)
Karnofsky Performance Status (Section 7)	X		
Targeted Physical Assessment (Section 7)	X		
Vital Signs: BP, HR, RR, weight (Section 7)	X		
Prior/Concomitant Medications (Section 7)	X	X	
Clinical Laboratory Evaluation (CBC, CMP, Mag, Phos, LDH) (Section 7)	X		
Urinalysis (Section 7)	X		
Clinical laboratory Evaluation – endocrine (TSH, T4) (Section 7)	X		
Urine Pregnancy Test (Section 7)	X		

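### Cohort B has no scheduled ADA sample before its first (neoadjuvant) INCAGN01876 dose, so ADA positivity at post-operative Cycle 1 Day 1 cannot be classed as pre-existing or induced; first-dose PK is also missing

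*Combined protocol and SAP*

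**What the plan says.** Section 2.1.3 sets an exploratory objective of learning whether antibodies form against INCAGN01876. The matching endpoint in Section 2.2.3 is "Detection of anti-drug antibodies (ADA) against INCAGN01876". Neither that section nor Section 8.2.2 defines treatment-emergent ADA or gives a rule for analysing it.

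In Cohort B, Section 3.1.2 places a dose before surgery: "In both surgical sub-arms, within 7 days of enrollment the subject will receive a single dose of the investigational systemic agent(s". A footnote to Table 9 confirms that both sub-arms get INCAGN01876 at that point: "the subject will be assigned to receive the combination of INCMGA00012 and INCAGN01876, or the combination of INCMGA00012 and INCAGN01876 plus SRS". The row "INCAGN01876 Administration (Section 5" accordingly carries a mark at neoadjuvant Day 1.

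The rows "Blood collected for INCAGN01876 ADA (Section 7" and "Blood collected for INCAGN01876 PK (Section 7" in Table 9 are blank until post-operative Cycle 1 Day 1. The row "Blood collected for correlatives (Section 7" does have a mark at neoadjuvant Day 1. On timing within the visit, the footnote reads "PK samples for INCAGN01876 collected pre-dose and at end of infusion on Cycle 1 Day 1 and Cycle 3 Day 15", and other PK draws are pre-dose. No such statement is made for ADA in Table 8 or Table 9. Section 7.9 sends the reader to these tables for the times of the correlative blood and adds no further ADA or PK time point.

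**The concern.** Table 8 and Table 9 use the same label, Cycle 1 Day 1, for different events. In Cohort A it is the day of first exposure. In Cohort B it is the first post-operative treatment day, after one dose has been given and weeks have passed. The ADA and PK rows start at that label in both tables, apparently without allowing for the added neoadjuvant dose.

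An objective about antibody formation asks for a change from before exposure. Without a sample from before the neoadjuvant dose, a Cohort B subject who is positive at Cycle 1 Day 1 may have carried the antibody at entry or may have made it in response to that dose. The data cannot separate the two, and the missing sample cannot be recovered once the subject has been dosed.

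For PK, the Cohort B samples at Cycle 1 Day 1 follow a second dose after a gap that varies between subjects. Reading them by visit label alongside Cohort A would mix first-dose and second-dose values.

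**Working it through.** **Step 1: read Table 9 row by row.** The four relevant rows each have 14 cells, matching the 14 columns of the header, so there is no sign of a column shift. Up to the first post-operative dose they read:

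| Row | Screen | Neoadj. Day 1 | Neoadj. Day 5 | Pre-Op | Post-Op | Cycle 1 Day 1 |
|---|---|---|---|---|---|---|
| INCAGN01876 dose | – | X | – | – | – | X |
| ADA | – | – | – | – | – | X |
| PK | – | – | – | – | – | X |
| Correlative blood | – | X | – | – | – | X |

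ADA is then drawn at Cycle 1 Day 15, Cycle 2 Day 15 and Day 15 of later cycles. The first ADA and PK samples therefore fall at the second INCAGN01876 dose.

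**Step 2: number of subjects.** The synopsis plans 16 + 16 = 32 subjects. Both sub-arms are dosed before surgery, so 16/32 = 50% have no designated pre-exposure ADA sample.

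**Step 3: gap from first dose to first ADA/PK sample.** The windows come from Section 3.1.2:
- sub-arm 2: surgery 7–14 days after drug;
- sub-arm 1: SRS starts 3–7 days after drug, and surgery follows 7–14 days after SRS (Section 1.5.2 counts this from completion of radiation);
- both: restart at most 35 days after surgery, with no stated minimum.

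From first to last fraction takes 2 days on consecutive days, or 4 days with the every-other-day option.

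- Sub-arm 2: shortest 7 + 0 = 7 days; longest 14 + 35 = 49 days.
- Sub-arm 1: shortest 3 + 2 + 7 + 0 = 12 days; longest 7 + 4 + 14 + 35 = 60 days (7 + 2 + 14 + 35 = 58 with consecutive-day fractions).

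The lower ends are nominal, since they assume no recovery time after surgery.

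**Step 4: what can and cannot be classified in Cohort B.**
- Negative at Cycle 1 Day 1, positive later: seroconversion on treatment, identifiable.
- Negative at every sample: no ADA detected, and no baseline is needed to say so.
- Positive at Cycle 1 Day 1: pre-existing or induced by the neoadjuvant dose, not separable. Any titre change is measured from an exposed sample.

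The first two lines assume that residual drug does not mask antibody in the assay; the documents do not describe its drug tolerance. The number falling in the third line is 16 × p, where p is the proportion positive at Cycle 1 Day 1. The documents give no value for p, so the number may be anything from 0 to 16.

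**Step 5: PK.** In Cohort A, the pre-dose and end-of-infusion samples at Cycle 1 Day 1 describe the first dose. In Cohort B the same pair describes the second dose, and the pre-dose sample may contain residual drug. The documents give no half-life for INCAGN01876, so the amount cannot be stated.

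**The case against.** The best case for leaving the plan alone has four parts.

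First, ADA is exploratory and the endpoint is worded as detection. Treatment-emergent ADA is nowhere defined, and Cohort A addresses formation from first exposure. This stands as a limit on importance. But the objective still asks whether antibodies form, and even Cohort A's Cycle 1 Day 1 ADA draw is not stated to be pre-dose.

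Second, a reader might infer that treatment-emergent ADA cannot be identified at all in half the trial. The documents do not support that: the later ADA draws allow seroconversion from a negative Cycle 1 Day 1 sample to be seen. The 50% counts subjects without a baseline, not subjects who cannot be classified.

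Third, the PK gap is easily overstated. A sample before any exposure should read zero in a drug-naive subject, so its absence costs little. What is missing is the first-dose profile. Nor does Section 8.2.2 specify any pooling of PK across cohorts. With recorded dose times and the measured pre-dose level, a PK model could use both. What remains is a labelling point: a summary by visit name should not mix the cohorts.

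Fourth, 60 mL of research blood is already drawn at neoadjuvant Day 1, and Section 7.9 allows further assays on stored samples. That is a possible back-up only, because the draw is neither designated for ADA nor stated to be pre-dose.

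**Conclusion.** The point holds at the level of an exploratory endpoint. Followed as written, the schedule gives none of the 16 Cohort B subjects a designated ADA sample before first exposure. Their first sample comes up to about 49 days (sub-arm 2) or 60 days (sub-arm 1) after the neoadjuvant dose. The loss is specific: the origin of any ADA already present at Cycle 1 Day 1, titre change from a true baseline, and first-dose PK. Detection of ADA and recognition of later seroconversion remain possible.

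How many subjects would be left unclassified depends on the positivity rate at Cycle 1 Day 1, which the documents do not give. The gap figures rest on the stated windows at their limits. The primary ORR analysis, which uses Cohort A only, is unaffected. The change is worth making because it is small and the sample cannot be obtained later.

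**What to change.** - In Table 9, add an ADA sample at neoadjuvant Day 1, taken with the correlative blood already scheduled. Specify that draw as pre-dose, and name the sample as the Cohort B ADA baseline.
- Mark ADA draws as pre-dose in both Table 8 and Table 9, since the present footnote covers PK only.
- Label Cohort B Cycle 1 Day 1 PK as second-dose, and do not summarise it with Cohort A first-dose PK.
- Optionally, add an end-of-infusion PK sample at neoadjuvant Day 1 if a first-dose profile is wanted in Cohort B. This is a new timed draw rather than an extra tube.

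The cost of the ADA change is one extra tube and one assay per Cohort B subject, 16 in all, at a visit and draw that already take place. Planned subjects with a pre-exposure ADA sample would rise from 16 of 32 to 32 of 32, provided that Cohort A's Cycle 1 Day 1 draw is made pre-dose as above.

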1.5.2. Stereotactic Radiosurgery

Subjects in Cohort A and in sub-arm #1 of Cohort B will receive hypofractionated radiation (stereotactic radiosurgery; SRS) to a dose of 8 Gy in 3 fractions. The dose of 8 Gy in 3 fractions was chosen based on preclinical evidence suggesting that it may maximally invoke an anti-tumor immune response (Vanpouille-Box, *Nature Communications*, 2017), compared to a variety of other fractionation schedules. For subjects treated in the nonsurgical cohort (Cohort A), a single dose of each systemic therapy (INCMGA00012 and INCAGN01876) is administered 3-7 days prior to SRS to prime the tumor immune microenvironment for optimal immune response to the SRS. Following SRS, the systemic agents are resumed according to their dosing schedule (i.e.,

INCMGA00012 is resumed 4 weeks from the date of the initial pre-SRS dose, and INCAGN01876 is resumed 2 weeks from the date of the initial pre-SRS dose). For the surgical arm (Cohort B; Surgical Sub-Arm #1 only), preclinical data suggests that in order to develop a maximal anti-tumor immune response the tumor needs to remain in situ for at least 7 days post radiation prior to surgical removal (De La Maza et al, *Clinical Cancer Research*, 2017). Thus, surgical resection (Cohort B; Surgical Sub-Arm #1 only) will take place 7-14 days following completion of radiation.

Overall, hypofractionated radiation has been shown to be safe and well-tolerated in recurrent GBM. For re-irradiation in general in recurrent GBM, the rate of grade 3 or higher AEs is less than 10% (Kazmi et al, *J Neurooncol* 2019). For SRS specifically in rGBM, prior studies have suggested a rate of grade 3 or higher AEs of ~3% (Holt et al, *J Cancer Res Ther* 2016; Clarke et al, *Int J Radiat Oncol Biol Phys* 2017). The rate of symptomatic radionecrosis from SRS in rGBM is estimated to be about 15-20% (Imber BS, et al, *Neurosurg* 2017).

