3.1.3.1. Safety Follow-Up

A scheduled safety follow-up visit occurs 30 (+/- 7) days after the EOT visit (the visit that occurs when subjects are taken off study treatment (see [Section 6](#); [Table 8](#) and [Table 9](#) for full schedule of events). Reasonable efforts should be made to have the subject return for the follow-up visit and report any AEs that may occur during this period. If the subject cannot return to the site for

the safety follow-up visit, the subject is contacted by telephone for collection of AEs and SAEs, and this should be documented in the eCRF.

Following the scheduled 30-day safety follow-up visit, subjects are contacted by telephone, e-mail or visit one additional time 12 weeks (+/- 14 days) from the EOT visit to capture additional immune related AEs (see sections 1.3.1.3 and 1.3.2.3).

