Adverse Event / Unanticipated Problems Assessment (Section 7)	X	X*	
MRI brain (tumor assessment) (Section 7)			X
Subject Vital Status (Collection of survival information every 3 months until death, lost to follow-up, or withdrawal of study consent)			X

* Only immune related Adverse Events are to be collected at the 12-week safety follow- up timepoint (see sections 1.3.1.3 and 1.3.2.3).

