9.1.2 Immune-Related Adverse Events

Immune-related AEs (irAEs) may be defined as an AE of unknown etiology, associated with drug exposure and consistent with an immune phenomenon. irAEs may be predicted based on the nature of the INCMGA00012 and INCAGN01876 compounds, their mechanism of action, and extensive reported experience with immunotherapies that have a similar mechanism of action.

Special attention should be paid to AEs that may be suggestive of potential irAEs. An irAE can occur shortly after the first dose or several months after the last dose of treatment.

Of note, intratumoral/peritumoral edema and any resultant AEs (seizure, e.g.), even if attributed to the study drug(s), are NOT considered irAEs in this study. Such edema may be a desired effect of the treatment, as it may represent immune infiltration of the tumor.

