9.2 Collecting and recording of Adverse Events

Adverse event collection will occur from signing of the informed consent form until the 12-week safety follow-up visit. At screening, any clinically significant abnormality should be recorded as a preexisting condition. At the 12-week safety follow-up, any new clinically significant findings/abnormalities that meet the definition of an immune related adverse event must also be recorded and documented as an adverse event (see sections 1.3.1.3 and 1.3.2.3).

At each contact with the subject, the investigator will seek information on adverse events by specific questioning and, as appropriate, by examination. AEs may also be volunteered spontaneously by the study patient. Information on all adverse events will be recorded immediately in the source document, and also in the appropriate adverse event module of the electronic case report form (eCRF).

Each AE should be evaluated to determine:

- The severity grade (CTCAE Grade 1 to 5).
- The start and end dates, unless unresolved at final follow-up.
- The action taken with regard to study drug(s)
- The event outcome (e.g, not recovered/not resolved, recovered/resolved, recovering/resolving, recovered/resolved with sequelae, fatal, unknown).
- The seriousness, as per serious adverse event (SAE) definition provided in [Section 9.1.2](#)
 - Per the Investigator, whether the event is definitely related, probably related, possibly related, unlikely related, or unrelated to the study drug(s) and/or SRS. In order to be unrelated, a causal relationship between the drug(s)/SRS and the AE is not a reasonable possibility: there is no temporal relationship between the medicinal product and event, or an alternative etiology is more reasonable.

All adverse events occurring between the time the informed consent form is signed and the end of the safety follow up phase will be recorded. The clinical course of each event will be followed until resolution, stabilization, or until it has been determined that the study intervention or participation is not the cause. Serious adverse events that are still ongoing at the 12-week safety follow-up period will continue to be followed to determine the final outcome.

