9.3 Reporting of Adverse Events

The study period during which adverse events must be reported is defined as the period from the signing of the informed consent form to the 12-week safety follow-up visit.

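### Table 10 and 3.1.3.1 limit the 12-week safety contact to irAEs while 9.2 and 9.3 cover all AEs, so late tumour edema and radionecrosis could be missed if Table 10 is followed

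*Combined protocol and SAP*

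**What the plan says.** Two places restrict the 12-week contact. The footnote to the AE row of Table 10 (section 6) reads "Only immune related Adverse Events are to be collected at the 12-week" timepoint. Section 3.1.3.1 describes the contact as made "one additional time 12 weeks (+/- 14 days) from the EOT visit to capture additional immune related AEs". The visit before it is not restricted: "A scheduled safety follow-up visit occurs 30 (+/- 7) days after the EOT visit", and Table 10 marks AE assessment there without a footnote.

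Two places do not restrict it. Section 9.2 opens by running AE collection from consent to the 12-week visit, and later says that "All adverse events occurring between the time the informed consent form is signed and the end of the safety follow up phase" will be recorded. Section 9.3 defines the reporting period as "the period from the signing of the informed consent form to the 12-week safety follow-up visit", with no limit to irAEs.

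Section 9.1.2 then narrows what an irAE is. Edema in or around the tumour and events resulting from it, with seizure given as the example, "even if attributed to the study drug(s), are NOT considered irAEs in this study". Section 12.1 names cerebral edema as the likeliest cause of a drug-related SAE, and 5.8.3 expects SRS to produce it. On the radiation side, 1.5.2 states: "The rate of symptomatic radionecrosis from SRS in rGBM is estimated to be about 15-20" percent. Radionecrosis is absent from the irAE list in 1.3.1.3.

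**The concern.** Frequency, duration and severity of AEs form a secondary endpoint (2.2.2). A site that works from Table 10 and a site data manager who works from section 9 would collect different data over the same interval, and both would be following the protocol. The difference is not neutral as to type of event. The narrower rule keeps the immune events and drops the edema-related and radiation-related ones, which the protocol itself expects from this combination.

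There are practical reasons to think that Table 10 would be used. Sections 3.2 and 6.2 both send subjects to follow-up according to that table. Its rule is the more specific one. The contact may be by telephone or e-mail, and Table 10 schedules no examination or laboratory tests for it. Section 9.2 says that AEs are sought by direct questioning, so what staff are told to ask about largely decides what is found.

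**Working it through.** The point rests on no sample size, power or event figure, so there is no figure in the plan to reproduce. The check sets the passages side by side and works out the length of the disputed interval.

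**Scope of collection at week 12**

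- Table 10 footnote: irAEs only.
- 3.1.3.1: the stated purpose is irAEs, which agrees with Table 10.
- 9.2, opening sentence: AE collection runs to the 12-week visit, with no restriction by type.
- 9.2, sentence on the 12-week contact: findings that meet the irAE definition must *also* be recorded. This adds irAEs to what is collected and does not say that nothing else is.
- 9.2, later sentence: all AEs to the end of safety follow-up. Table 10 labels its 12-week column as the safety follow-up, so the end point is the same contact.
- 9.3: reporting period to the 12-week visit, with no restriction by type.

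The first two and the last four cannot both be applied to a non-immune AE that first arises after the 30-day visit. No passage ranks them, and 8.2.2 gives no AE time window for the safety analysis.

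**What the narrow rule leaves out**

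- Tumour-related edema and its consequences: excluded from irAEs by 9.1.2, even if drug-attributed.
- Radionecrosis: not listed in 1.3.1.3.
- The Table 10 footnote sends the reader to 1.3.1.3 and 1.3.2.3 for the meaning of irAE, not to 9.1.2, where the edema exclusion sits. The footnote is therefore not tied to the definition that 8.2.2 uses when it refers to section 9.

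**Length of the disputed interval**

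Inputs from 3.1.3.1 and Table 10, both counted from the EOT visit: first safety visit at 30 ± 7 days, that is day 23 to 37; second contact at 12 weeks ± 14 days, that is 84 ± 14, or day 70 to 98.

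- Nominal: 84 − 30 = 54 days.
- Shortest: 70 − 37 = 33 days.
- Longest: 98 − 23 = 75 days.

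**Number of events affected**

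This would need the share of edema and radionecrosis that first appears in that interval after EOT. The documents give no onset timing for either, so no number follows.

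**The case against.** The strongest reply is that nothing is necessarily lost. If section 9 governs, edema and radionecrosis are recorded to week 12, and the *also* in 9.2 favours that broader reading. AEs of every kind are assessed at treatment visits, at EOT and at the 30-day visit. Serious events have a separate route: 9.3.2 requires SAEs to reach the sponsor within 24 hours, the 9.3 reporting period runs to week 12, and SAEs still open then are followed to outcome. An unscheduled visit for an AE is recorded like any other visit (6.1), and subjects off drug without progression have MRI every 12 weeks (3.1.3.2). Limiting late off-treatment collection to irAEs could also be a defensible choice if the protocol made it consistently.

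Most of this stands. It confines the gap mainly to new, non-serious events that prompt no unscheduled visit. It does not remove the contradiction, because the reply works only if one set of passages is preferred and the protocol does not say which.

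A reader might also infer that the main expected toxicity certainly goes uncounted after day 30 and that the safety endpoint is biased downward. The documents do not support that. The loss depends on Table 10 and 3.1.3.1 being followed, and the clock starts at the EOT visit, not at the start of treatment. Nor can the cited radionecrosis rate be multiplied by the 16 + 8 = 24 planned SRS recipients to give cases missed. That rate carries no timing, and the eight in Cohort B sub-arm 1 have their tumour resected 7 to 14 days after SRS (3.1.2), so a general rate for SRS in recurrent disease cannot simply be applied to them.

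**Conclusion.** Wrong as written: this is an internal contradiction. Table 10 and 3.1.3.1 say one thing about the 12-week contact, 9.2 and 9.3 say another, and nothing settles it. If Table 10 is followed, new tumour edema, its consequences and radionecrosis arising after the 30-day post-EOT visit could be missed for a nominal 54 days per subject (33 to 75 with windows), mainly where they are non-serious. Any error would then run toward under-counting. The number of events cannot be stated. The primary endpoint is not affected.

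The conclusion assumes that staff would ask only about what the governing text tells them to collect, and that radionecrosis would not be classed as an irAE. The second assumption rests on its absence from the list in 1.3.1.3; no sentence excludes it expressly.

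**What to change.** Reconcile the Table 10 footnote and 3.1.3.1 with 9.2 and 9.3, so that one rule applies at the 12-week contact. The simplest form is to record all AEs there. At minimum it should record irAEs, all SAEs, and any AE possibly related to study drug or SRS, naming edema, seizure and radionecrosis. Point the footnote to 9.1.2 for the irAE definition. State the same AE window for the safety tables in 8.2.2.

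The change concerns data collection only and leaves treatment untouched. It costs a few more questions, and the recording of the answers, at a contact already scheduled.
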